5. Pharmacokinetic samples for GSK3342830 and potential metabolites will be collected on Day 1 at the following time points: pre-dose (within 15 minutes before dosing) and 0.5, 1 (end of infusion), 1.25, 1.5, 2, 2.5, 3, 3.5, 4, 4.5, 5, 6, 8, 10, 12, 16, and 24 hours after the start of infusion. Single pre-dose trough samples will be taken on the mornings of Days 3, 6, 9, 12, and 13. Serial samples will be collected on Day 15 at the following time points: pre-dose (within 15 minutes before dosing) and 0.5, 1 (end of infusion), 1.25, 1.5, 2, 2.5, 3, 3.5, 4, 4.5, 5, 6, and 8 hours after the start of infusion. At the end of the study, the saved blood samples from a predicted therapeutically-relevant dose level and higher dose level for plasma PK analysis of parent and from the highest dose level completed for potential metabolite profile will be transferred to a GSK specified laboratory. Details of PK sample

collection and storage will be provided in the Study Reference Manual.

6. Pooled urine samples will be collected on Day 1 and Day 15 over the following time intervals: pre-dose (within a 24-hour period before dosing, may begin on Day -1) and 0 to 8 and 8 to 24 hours post-dose. Two aliquots of urine samples for baseline analysis may be collected from any time after admission to just before dosing on Day 1. At the end of the study, the saved urine samples from a predicted therapeutically-relevant dose level and higher dose level for urinary PK analysis of parent and from the highest dose level completed for potential metabolite profile, will be transferred to a GSK specified laboratory. Urine will be collected in opaque bottles to maintain blind of blinded study site personnel. Details of urine sample collection and storage will be provided in the Study Reference Manual.
7. Continuous dual-lead telemetry will be initiated on Day -1 at least 8 hours before treatment administration on Day 1 and will continue until 48 hours post dose.
8. Subjects will be discharged from the clinical unit after the Day 16 assessments are complete.

Table 6 Time and Events Table: Follow-up Visit; Single and Repeat Dose Escalation (Part 1 and Part 2) and Single Dose (Part 3)

Procedure	Follow-up Visit (7 to 10 days post last dose or early termination)
Adverse event/serious adverse event review	X
Concomitant medication review	X
Brief physical examination	X
12-lead electrocardiogram	X
Vital signs	X

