9.4. Key Elements of Analysis Plan

9.4.1. Primary Analyses

Safety Analyses

The following safety evaluations will be performed:

- Monitoring for AEs
- Routine clinical laboratory tests including chemistry, hematology, and urinalysis
- Vital signs
- Twelve-lead ECG readings
- Continuous cardiac monitoring (dual-lead telemetry)

Safety endpoints will include AEs, clinical laboratory test results (chemistry [including liver function parameters], hematology, and urinalysis), vital signs (BP, heart rate, respiratory rate, and body temperature), and 12-lead ECG readings.

All safety data will be presented in data listings. Subject demographics, medical history, and prior and concomitant medications will be summarized for each dose level using descriptive statistics. For continuous variables, these summaries will include number of subjects, mean, median, standard deviation, minimum, and maximum.

For categorical variables, the summaries will include frequencies and corresponding percentages. No inferential hypothesis testing will be performed on the safety variables.

Adverse events will be coded using the MedDRA classification system.

Treatment-emergent AEs will be defined as any AEs, regardless of relationship to study drug, that occur after the dose of study drug until the Follow-up visit. The treatment-emergent AEs will be summarized for each dose level at AE onset for the overall number of AEs and percentage of subjects who experience them. The total number of AEs will be summarized by dose level and overall. The AEs will be further summarized by severity and relationship to the study drug. If relationship information is missing, the AE will be considered treatment related. Listings for the subsets of SAEs

and treatment-related SAEs will be provided. The SAEs and number of AEs leading to discontinuation will be summarized. The incidence of AEs will also be summarized by system organ class and preferred term.

Clinical laboratory test results, vital signs, and 12-lead ECG results will be summarized by actual values and change from baseline. Clinical laboratory values that are outside of the reference ranges will be flagged and evaluated for clinical significance by the investigator. Any 12-lead ECG abnormalities will be summarized by each dose level. Physical examination findings and cardiac telemetry results will be listed.

Detailed descriptions of the analyses in this study will be presented in the RAP.

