## 7. PRIMARY STATISTICAL ANALYSES

### 7.1. Safety Analyses

#### 7.1.1. Overview of Planned Safety Analyses

The safety analyses will be based on the Safety population, unless otherwise specified.

Table 3 provides an overview of the planned Safety analyses, with full details of data displays being presented in Appendix 11: List of Data Displays.

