
 
• Reporting for tables, figures and formal statistical analyses :             
 
• Planned time relative to dosing will be used in figures, summaries, statistical analyses and calculation of any derived parameters, unless otherwise stated.
 
• The impact of any major deviation from the planned assessment times and/or scheduled visit days on the analyses and interpretation of the results will be assessed as appropriate.
 
 
 
• Reporting for Data Listings:             
 
• Planned and actual time relative to study drug dosing will be shown in listings (Refer to IDSL Statistical Principle 5.05.1).
 
• Unscheduled or unplanned readings will be presented within the subject's listings.
 
• Visits outside the protocol defined time-windows (i.e. recorded as protocol deviations) will be included in listings but omitted from figures, summaries and statistical analyses.
 
 
 
	
Unscheduled Visits	

 
• Unscheduled visits will not be included in summary tables.
 
• Unscheduled visits will not be included in figures.
 
• All unscheduled visits will be included in listings.
 
	
Descriptive Summary Statistics	
Continuous Data	Refer to IDSL Statistical Principle 6.06.1
Categorical Data	N, n, frequency, %
Reporting of Pharmacokinetic Concentration Data	
Descriptive Summary Statistics	Refer to IDSL Statistical Principle 6.06.1 Assign zero to NQ values (Refer to GUI_51487 for further details)
Reporting of Pharmacokinetic Parameters	
Descriptive Summary Statistics (Log Transformed)	N, n, geometric mean, 95% CI of geometric mean, standard deviation (SD) of logged data and between geometric coefficient of variation (CV b - (%)) will be reported. $CV_b (\%) = \sqrt{(\exp(SD^2) - 1) * 100}$ (SD = SD of log transformed data)

Reporting Standards	
Parameters Not Being Log Transformed	Tmax, %AUCex, tlast, lambda_z, lambda_z_lower, lambda_z_upper, lambda_z_no. of points, Ratio of time invariance, Ratio of accumulation, Feu(t1-t2), CLr, Ae
Listings	Include all following PK parameters: Cmax, AUC0-∞, AUC0-t, AUC(0-τ), t1/2, CL, Vss, Cτ, Ratio of time invariance, Ratio of accumulation, Tmax, %AUCex, tlast, lambda_z, lambda_z_lower, lambda_z_upper, lambda_z_no. of points, Feu(t1-t2), CLr, Ae.
Graphical Displays	

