**CONFIDENTIAL**

204847

ICH : Listings					
No.	Population	IDSL / TST ID / Example Shell	Title	Programming Notes	Deliverable [Priority]
12	Safety	AE8	Listing of All Adverse Events		SAC [1]
13	Safety	AE8	Listing of Drug-Related Adverse Events		SAC [1]
14	Safety	SAFE_L2	Listing of Serious Adverse Events		SAC [1]
15	Safety	AE8	Listing of Adverse Events Leading to Withdrawal from Study		SAC [1]
16	Safety	SAFE_L3	Listing of Infusion Site Reaction Adverse Events	Conditional display	SAC [1]
17	Safety	SAFE_L4	Listing of Liver Adverse Events	Conditional display	SAC [1]
18	Safety	SAFE_L5	Listing of Cardiovascular Adverse Events	Conditional display	SAC [1]
19	Safety	SAFE_L8	Listing of Rash Events	Conditional display	SAC [1]
Laboratory Measurements					
20	Safety	LB5	Listing of Clinical Chemistry Toxicities of Grade 3 or Higher		SAC [1]
21	Safety	LB5	Listing of All Clinical Chemistry Data for Subjects with Toxicities of Grade 3 or Higher		SAC [1]
22	Safety	LB5	Listing of Haematology Toxicities of Grade 3 or Higher		SAC [1]
23	Safety	LB5	Listing of All Haematology Data for Subjects with Toxicities of Grade 3 or Higher		SAC [1]
24	Safety	UR2a	Listing of Urinalysis Toxicities of Grade 3 or Higher		SAC [1]
25	Safety	UR2a	Listing of Urinalysis Data for Subjects with Toxicities of Grade 3 or Higher		SAC [1]
ECGs					
26	Safety	EG5	Listing of Abnormal ECG Findings		SAC [1]
27	Safety	EG5	Listing of All ECG Findings for Subjects with an Abnormal Finding		SAC [1]
28	Safety	EG3	Listing of ECG Values of Potential Clinical Importance		SAC [1]

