**CONFIDENTIAL**

204847

ICH : Listings					
No.	Population	IDSL / TST ID / Example Shell	Title	Programming Notes	Deliverable [Priority]
29	Safety	EG3	Listing of All ECG Values for Subjects with Any Value of Potential Clinical Importance		SAC [1]
Vital Signs					
30	Safety	VS4	Listing of Vital Signs of Potential Clinical Importance		SAC [1]
31	Safety	VS4	Listing of All Vital Signs for Subjects with Potential Clinical Importance Values		SAC [1]
Liver Events					
32	Safety	LIVER5	Listing of Liver Monitoring/Stopping Event Reporting	Conditional display	SAC [1]
33	Safety	MH3	Listing of Medical Conditions for Subjects with Liver Stopping Events	Conditional display	SAC [1]
34	Safety	SAFE_L9	Listing of Alcohol Intake at Onset of Liver Event	Conditional display	SAC [1]
35	Safety	PKCL1X	Listing of Plasma Concentration Data for Subjects with Liver Stopping Events	Conditional display	SAC [1]
36	Safety	LIVER7	Listing of Liver Biopsy Details	Conditional display	SAC [1]
37	Safety	LIVER8	Listing of Liver Imaging Details	Conditional display	SAC [1]
Cardiac Telemetry					
38	Safety	SAFE_L10	Listing of Cardiac Telemetry Monitoring		SAC [1]
39	Safety	SAFE_L11	Listing of Cytokine Data		SAC [1]
Pharmacokinetic Concentration					
40	PK	PKCL1X	Listing of GSK3342830 Pharmacokinetic Plasma Concentration-Time Data by Treatment in Part 1 and Part 3		SAC [1]
41	PK	PKUL1P	Listing of GSK3342830 Pharmacokinetic Urine Concentration-Time Data by Treatment in Part 1 and Part 3		SAC [1]

[figure not shown]

ICH : Listings					
No.	Population	IDSL / TST ID / Example Shell	Title	Programming Notes	Deliverable [Priority]
42	PK	PKCL1X	Listing of GSK3342830 Pharmacokinetic Plasma Concentration-Time Data by Treatment in Part 2		SAC [1]
43	PK	PKUL1P	Listing of GSK3342830 Pharmacokinetic Urine Concentration-Time Data by Treatment in Part 2		SAC [1]
Pharmacokinetic Parameter					
44	PK Parameter	PLPL1X	Listing of GSK3342830 Plasma Pharmacokinetic Parameters by Treatment in Part 1 and Part 3		SAC [1]
45	PK Parameter	PLPL1X	Listing of GSK3342830 Urine Pharmacokinetic Parameters by Treatment in Part 1 and Part 3		SAC [1]
46	PK Parameter	PLPL1X	Listing of GSK3342830 Plasma Pharmacokinetic Parameters by Treatment in Part 2		SAC [1]
47	PK Parameter	PLPL1X	Listing of GSK3342830 Urine Pharmacokinetic Parameters by Treatment in Part 2		SAC [1]

Figure 2.1

Part: xx  
Cytokine Parameter (Unit)

[figure not shown]

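### Late Follow-up visits are dropped from the visit-based safety tables, and the SAP's trigger-restricted listings leave some of those values in no output

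*SAP*

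**What the plan says.** The rule is in SAP 10.3.3, under planned and actual time: "Visits outside the protocol defined time-windows (i.e. recorded as protocol deviations) will be included in listings but omitted from figures, summaries and statistical analyses". The same section keeps unscheduled visits out of summary tables and figures and sends them to listings.

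The window that matters is the Follow-up visit. The column heading of Protocol 7.1, Table 6 begins "Follow-up Visit (7 to 10 days post last dose or early termination".

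On listings, Protocol 9.4.1 sets no threshold: "All safety data will be presented in data listings". SAP 2.1 declares no change from the protocol's analysis plan. SAP Table 3 marks an individual listing for chemistry, haematology, urinalysis, ECG and vital signs, but SAP 7.1.1 introduces that table as an overview, "with full details of data displays being presented in Appendix 11: List of Data Displays".

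Appendix 11 (SAP 10.11.9) then specifies only restricted listings for these data types:
- Listing 20 is "Listing of Clinical Chemistry Toxicities of Grade 3 or Higher". Its wider companion, Listing 21, is "Listing of All Clinical Chemistry Data for Subjects with Toxicities of Grade 3 or Higher".
- Listing 23, the wider haematology listing, is "Listing of All Haematology Data for Subjects with Toxicities of Grade 3 or Higher". Listings 24 and 25 do the same for urinalysis.
- Listings 26 and 27 cover abnormal ECG findings and the subjects who have one. Listings 28 and 29 cover ECG values of potential clinical importance and those subjects.
- Listing 30 is "Listing of Vital Signs of Potential Clinical Importance". Listing 31 gives all vital signs for the same subjects.

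**The concern.** Leaving off-schedule values out of nominal-time summaries is defensible if the values can be seen elsewhere. Here the place they are sent to is conditional. A measurement that was taken, recorded and valid can end up shown nowhere because the visit was late and the subject had no marked abnormality.

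Safety is the primary endpoint and is purely descriptive, so what the tables and listings show is the whole result. Follow-up is the only scheduled assessment after discharge on Day 3 (Parts 1 and 3) or Day 16 (Part 2). It carries most of the scheduled information on whether smaller shifts persist or recover.

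**Working it through.** The plan states no figure to reproduce on this point. The check compares the rule with the list of displays and then counts what one late Follow-up removes.

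**Step 1: which tables lose the value.** Safety tables run from 2.1 to 2.17 (SAP 10.11.5). Tables 2.1 to 2.5 are adverse event tables and do not depend on visit windows. Tables 2.6 to 2.17 summarise laboratory, ECG and vital-sign measurements: 17 − 6 + 1 = 12 of 17 tables. The only safety figures planned are for cytokines.

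**Step 2: which listings can still show it.**

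| Data type | Widest listing | Condition for a subject to appear |
|---|---|---|
| Chemistry | 21 | a Grade 3 or higher chemistry toxicity |
| Haematology | 23 | a Grade 3 or higher haematology toxicity |
| Urinalysis | 25 | a Grade 3 or higher urinalysis toxicity |
| ECG findings | 27 | an abnormal finding |
| ECG values | 29 | a value of potential clinical importance |
| Vital signs | 31 | a value of potential clinical importance |

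A subject who meets no condition for a data type has no listing of that type. Important protocol deviations reach Table 1.4 and Listing 4, but those shells carry no measured value.

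**Step 3: how far down the triggers reach.** Haemoglobin of 95 to 99 g/L and platelets of 75 to 99.999 × 10⁹/L meet the treatment-stopping values in Protocol 5.4.2, yet both are Grade 1 in SAP Appendix 7. Total iron, total iron binding capacity, ferritin and reticulocytes have no grade there, so they cannot trigger a listing themselves. SAP 10.6.2 gives limits for blood pressure and heart rate but none for temperature.

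**Step 4: what one late Follow-up removes.**
- Laboratory, Parts 1 and 3: the post-dose points in the Table 2.6 shell are Day 2 and Follow-up. Loss = 1/2 = 50% of that subject's post-dose points.
- Laboratory, Part 2: Days 2, 5, 10, 15 and Follow-up. Loss = 1/5 = 20%.
- Iron, iron-binding capacity, ferritin and reticulocytes, Parts 1 and 3: Protocol Table 7, note 1 schedules Day −1 and Follow-up only. Loss = 1/1, all post-dose data. Protocol 4.6.1 names these tests as the monitoring for iron binding by the catechol side chain.
- ECG and vital signs, Parts 1 and 3: eight Day 1 points, Day 2, Day 3 and Follow-up make 11. Loss = 1/11 = 9%.
- Follow-up row for an active group: Part 1, 1/6 = 16.7%; Parts 2 and 3, 1/8 = 12.5% (about 6 and about 8 active per cohort, Protocol 4.3).

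**The case against.** The strongest reply is that the gap is narrow and that other routes catch what matters. Much of this stands:

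- Abnormal results that the investigator judges clinically significant are adverse events (Protocol 12.5.1). They reach Listing 12 with onset, resolution and outcome.
- Any abnormal ECG finding, including one judged not clinically significant, reaches Listing 26, and the subject's other findings reach Listing 27.
- A late value can itself be the trigger. Once a subject is triggered, all data of that type are listed.
- Subjects are confined through the dosing period, and the protocol gives no windows for post-dose safety time points during the stay. In practice the rule bites at Follow-up.
- The stopping values in Step 3 govern treatment, which has normally ended by Follow-up. They show only how far the listing triggers lie from values the protocol treats as notable.
- Omitting off-window values keeps each summary row homogeneous in time.

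Three further defences are weaker. SAP 10.3.3 says the impact of major timing deviations will be assessed as appropriate, but this creates no display. Protocol 7.3.7 has clinically significant laboratory results repeated until they settle, but such repeats are unscheduled readings and face the same listing restriction. Table 3 marks listings without a threshold, but it defers to Appendix 11.

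A reader might infer that late attendance tracks poor health, so that the rule selects against bad outcomes. That is plausible, but neither document says so, and neither gives an attendance or deviation rate.

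**Conclusion.** The concern holds for a defined set of values: laboratory, ECG and vital-sign measurements from an out-of-window visit, in practice Follow-up, that are not adverse events and belong to a subject who meets no listing trigger for that data type. For these, Appendix 11 contradicts both SAP 10.3.3 and Protocol 9.4.1.

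Two stronger readings are not supported. The rule does not empty every safety summary: the five adverse event tables are untouched. Nor does every dropped value disappear: triggered values and triggered subjects remain listed. Telemetry and cytokine listings are not threshold-restricted.

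Per late visit, the loss is half of a subject's post-dose laboratory points in Parts 1 and 3, a fifth in Part 2, and all post-dose results for the four iron-related tests in Parts 1 and 3. How often this would happen cannot be estimated from the documents. The conclusion assumes that Appendix 11 is the complete display list, as SAP 7.1.1 indicates, and that the sponsor's reporting standards cited in SAP 10.3.3, which are not reproduced there, add no unrestricted listings. The change should be made: it affects what the primary safety displays show, and it is cheap.

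**What to change.** 1. In SAP 10.3.3, state that for safety data a late Follow-up is assigned to the Follow-up visit, included in the summary and change-from-baseline tables, and flagged. Keep the exclusion only for time-matched PK concentration summaries. SAP 10.4.1 already has a closest-to-target rule for two values within a window, so this extends existing logic.
2. In Appendix 11, make the laboratory, ECG and vital-sign listings unrestricted, with actual times and an out-of-window flag. This meets Protocol 9.4.1 and also covers unscheduled readings, which the first change alone would leave unseen.

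The cost is a sentence in the SAP, revised listing titles and shells, and a windowing step in programming. The downside is slightly mixed timing within the Follow-up row and longer listings.

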**10.4.1. General**

Multiple Measurements at One Time Point

 
• Mean of the measurements will be calculated and used in any derivation of summary statistics but if listed, all data will be presented.
 
• If there are two values within a time window the value closest to the target day for that window will be used. If values are the same distance from the target then the mean will be taken.
 
• Subjects having both High and Low values for Normal Ranges at any post-baseline visits for safety parameters will be counted in both the High and Low categories of “Any visit post-baseline” row of related summary tables. This will also be applicable to relevant Potential Clinical Importance summary tables.
 

Study Day

 
• Calculated as the number of days from treatment date :             
 
• Ref Date = Missing → Study Day = Missing
 
• Ref Date < Treatment Date → Study Day = Ref Date – Treatment Date
 
• Ref Date ≥ Treatment Date → Study Day = Ref Date – (Treatment Date) + 1
 
 
 

**10.4.2. Study Population**

Demographics
Age

 
• GSK standard IDSL algorithms will be used for calculating age where birth date will be imputed as follows:             
 
○ Any subject with a missing day will have this imputed as day ‘15’.
 
○ Any subject with a missing date and month will have this imputed as ‘30th June’.
 
 
 
• Birth date will be presented in listings as ‘YYYY’.
 

Body Mass Index (BMI)

 
• Calculated as Weight (kg) / [Height (m)]
 

**10.4.3. Safety**

ECG Parameters
RR Interval

 
• IF ECG values are machine read and RR interval (msec) is not provided directly, then RR interval can be derived as :             
 
[1] If QTcB is machine read & RR is not provided, then :                 <math display="block">RR = \left[ \left( \frac{QT}{QTcB} \right)^2 \right] * 1000</math> 
 
[2] If QTcF is machine read and RR is not provided, then:
 
 
 

ECG Parameters
$RR = \left[ \left( \frac{QT}{QT_{cF}} \right)^3 \right] * 1000$

 
• If ECGs are manually read, the RR value preceding the measurement QT interval should be a collected value THEN do not derive.
 
• Important Note: Machine read values of RR should not be replaced with re-derived values.
 

Corrected QT Intervals

 
• When not entered directly in the eCRF, corrected QT intervals by Bazett's (QTcB) and Fredericia's (QTcF) formulas will be calculated, in msec, depending on the availability of other measurements.
 
• IF RR interval (msec) is provided then missing QTcB and/or QTcF will be derived as :
 

$QT_{cB} = \frac{QT}{\sqrt{\frac{RR}{1000}}} \qquad \qquad \qquad QT_{cF} = \frac{QT}{\sqrt[3]{\frac{RR}{1000}}}$

 
• Important Note: Machine read values of QTcB and QTcF should not be replaced with re-derived values. If neither machine read QTcB or QTcF are available but QT and RR are collected, then a QTcB and QTcF can be derived however this should be discussed and agreed with the study team and the TLFs must have an appropriate footnote denoting those parameters are derived.
 

Adverse Events
AE'S OF Special Interest

 
• Liver events
 
• CV events
 
• Infusion site reactions
 
• Potential systemic allergic reactions
 
• Hematologic events
 
• Rash Events
 

## 10.5. Appendix 5: Premature Withdrawals and Handling of Missing Data

### 10.5.1. Premature Withdrawals

Element	Reporting Detail
General	
 
• Subject study completion (i.e. as specified in the protocol) was defined as one who has completed all phases of the study including the follow-up visit.
 
• Withdrawn subjects may be replaced in the study.
 
• All available data from subjects who were withdrawn from the study will be listed and all available planned data will be included in summary tables and figures, unless otherwise specified.
 

### 10.5.2. Handling of Missing Data

Element	Reporting Detail
General	
 
• Missing data occurs when any requested data is not provided, leading to blank fields on the collection instrument : 
 
○ These data will be indicated by the use of a “blank” in subject listing displays. Unless all data for a specific visit are missing in which case the data is excluded from the table.
 
○ Answers such as “Not applicable” and “Not evaluable” are not considered to be missing data and should be displayed as such.
 
 
 

Outliers	
 
• Any subjects excluded from the summaries and/or statistical analyses will be documented along with the reason for exclusion in the clinical study report.
 

